6.6.2 Laboratory evaluation

For laboratory data assessments, data from all sources (central and local laboratories) will be combined. All laboratory assessments will be listed and those collected outside of the on- treatment period will be flagged in the listings. All laboratory values will be converted into SI units.

All the lab analysis over core and extension phase will be based on safety set. Study baseline will be used in analysis.

Laboratory data will be classified into CTC grades according to the NCI Common Terminology Criteria for Adverse Events CTCAE) v4.03. A severity grade of 0 will be assigned for all non-missing values not graded as 1 or higher. Grade 5 will not be used.

For some laboratory tests, CTC grades are defined in two directions (low and high, e.g. for potassium: hypokalemia and hyperkalemia). The two directions will be analyzed separately.

The following summaries will be produced for the laboratory data (by laboratory parameter and direction of abnormality, as applicable) over core (baseline to week 35) and extension phase (from week 43 to final cutoff) for safety set:

- Shift tables using CTC grades to compare baseline to the worst post-baseline value.
- For laboratory test where NCI-CTCAE v4.03 grades are not defined, shift tables using the low/normal/high/ (low and high) classification will be produced/used to compare baseline to the worst on-treatment value.
- Listing of all laboratory data with values flagged to show the corresponding NCI - CTCAE v4.03 grades and the classifications relatives to the laboratory

normal ranges.

Patients with laboratory values outside the normal range will be listed and flagged to show the corresponding CTC grades and the classifications relative to the laboratory reference ranges. In addition, laboratory values of patients with laboratory abnormalities of CTC grade 3 or 4 will be presented in separate listings.

Liver function tests (LFTs) of interest are total bilirubin (TBILI), ALT, AST and ALP. LFTs will be summarized over core and extension phase based on safety set:

- Shift tables of baseline vs. worst post-baseline on-treatment values for the categories:
 - $TBILI \leq 2xULN$, $TBILI > 2xULN$ and missing TBILI
 - $ALT \leq 3xULN$, $ALT > 3xULN$ and missing ALT
 - $AST \leq 3xULN$, $AST > 3xULN$ and missing AST
 - ALT or $AST \leq 3xULN$, ALT or $AST > 3xULN$ and missing ALT or AST
 - $ALP < 2xULN$, $ALP \geq 2xULN$ and missing ALP
- Frequency counts and percentages of patients with worst post -baseline on-treatment values in the categories:
 - $ALT > 3xULN$, $ALT > 5xULN$, $ALT > 10xULN$, $ALT > 20xULN$
 - $AST > 3xULN$, $AST > 5xULN$, $AST > 10xULN$, $AST > 20xULN$
 - AST or $ALT > 3xULN$, AST or $ALT > 5xULN$, AST or $ALT > 10xULN$, AST or $ALT > 20xULN$
 - $TBILI > 2xULN$
 - Concurrent $ALT > 3xULN$ and $TBILI > 2xULN$
 - Concurrent $AST > 3xULN$ and $TBILI > 2xULN$
 - Concurrent AST or $ALT > 3xULN$ and $TBILI > 2xULN$
 - Concurrent AST or $ALT > 3xULN$ and $TBILI > 2xULN$ and $ALP < 2xULN$
 - Concurrent AST or $ALT > 3xULN$ and $TBILI > 2xULN$ and $ALP \geq 2xULN$

Concurrent measurements are those occurring on the same date.

In addition, a listing of all TBILI, ALT, AST and ALP values for patients with a post-baseline TBILI > 2xULN, ALT > 3xULN or AST > 3xULN will be provided.

Renal Disease (MDRD) will be summarized over core and extension phase based on safety set:

- Shift tables of baseline vs. worst post-baseline on-treatment values
- Frequency counts and percentages of patients with worst post-baseline on-treatment values

The minimum of all the post baseline assessments is the worst value for MDRD.

For calcium, the corrected calcium will be used for analysis. Corrected calcium will be derived using the reported total calcium value and albumin at the same assessment using the following formula:

$$\text{Corrected Calcium (mg/dL)} = \text{Calcium (mg/dL)} - 0.8 [\text{Albumin (g/dL)} - 4]$$

In order to apply the above formula, albumin values in g/L will be converted to g/dL by multiplying by 0.1), calcium values in mmol/L will be converted to mg/dL by dividing by 0.2495. For calculation of laboratory CTC grades 0 and 1, the normal range for derived corrected calcium is set to the same limits (in mg/dL) as for calcium.

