Patients who had a baseline mUFC between 1.5 to 5 x ULN showed a greater response rate than patients with a baseline mUFC > 5x ULN (27.2% vs. 8.2%, respectively). Uncontrolled patients (those who did not normalize UFC and had less than 50% reduction from baseline in UFC) could be identified early in the treatment course with a high degree of certainty. Approximately 90% of patients with uncontrolled mUFC at both Months 1 and 2 were also uncontrolled at Months 6 and 12.

Pasireotide was well-tolerated. The majority of AEs were consistent with the known adverse drug reactions of Somatostatin Analogs (SSAs). The most common AEs (incidence  $\geq 10\%$ ) were diarrhea, nausea, abdominal pain, cholelithiasis, hyperglycemia, diabetes mellitus, fatigue and glycosylated hemoglobin increased. Hyperglycemia-related AEs appeared to be the most significant safety concern in terms of frequency of occurrence as well as overall clinical impact (i.e. overall increase in HbA1c of  $\sim 1.5\%$  for both dose groups at 6 and 12 months). Hyperglycemia was managed with the addition or adjustment in oral antidiabetic treatment or in some cases the addition of insulin. Patients who had pre-existing diabetes had a higher degree of hyperglycemia. As expected in successful therapies for hypercortisolism, AEs related to cortisol withdrawal (hypocortisolism) were reported in 13 (8.0%) patients, for which a dose decrease resulted in effective management of the AE.

Overall, pasireotide demonstrated a favorable benefit/risk profile in Cushing's disease. Importantly, patients that are relatively poor responders to pasireotide can be identified early

[figure not shown]
(i.e. after two months of treatment) with a high degree of certainty, thereby giving the option of prompt discontinuation of patients not likely to derive benefit from this drug.

Preliminary data (Feelders 2010) indicate synergic effect between pasireotide and cabergoline in increasing the biochemical control rate in patients with CD. When cabergoline was added to pasireotide in a proof of concept study, UFC normalization increased from 29% to 53%. These preliminary data make cabergoline the best partner for pasireotide in increasing biochemical control rate.

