## 5.2 Exclusion criteria

Patients must not meet any of the following exclusion criteria at screening:

1. Patients with compression of the optic chiasm causing any visual field defect that requires surgical intervention
2. Diabetic patients with poor glycemic control as evidenced by HbA1c >8%
3. Patients with risk factors for torsade de pointes, i.e. patients with a baseline QTcF >450 ms in males, and > 460 ms in females. hypokalemia, hypomagnesaemia, uncontrolled hypothyroidism, family history of long QT syndrome, or concomitant medications known to prolong QT interval
4. Patients with clinically significant valvular disease
5. Patients with Cushing's syndrome due to ectopic ACTH secretion
6. Patients with hypercortisolism secondary to adrenal tumors or nodular (primary) bilateral adrenal hyperplasia
7. Patients who have a known inherited syndrome as the cause for hormone over-secretion (i.e. Carney Complex, McCune-Albright syndrome, MEN-1)
8. Patients who are hypothyroid and not on adequate replacement therapy
9. Patients with symptomatic cholelithiasis
10. Patients who have congestive heart failure (NYHA Class III or IV), unstable angina, sustained ventricular tachycardia, clinically significant bradycardia, advanced heart block, history of acute MI less than one year prior to study entry or clinically significant impairment in cardiovascular function
11. Patients with liver disease such as cirrhosis, chronic active hepatitis, or chronic persistent hepatitis, or patients with ALT/AST > 2 X ULN, serum bilirubin >2.0 X ULN
12. Patients with serum creatinine >2.0 X ULN
13. Patients with WBC <3 X 10^9/L; Hb 90% < LLN; PLT <100 X 10^9/L
14. Patients who have a history of alcohol or drug abuse in the 6 month period prior to receiving pasireotide
15. Patients who have participated in any clinical investigation with an investigational drug within 1 month prior to dosing
16. Patients with active malignant disease within the last five years (with the exception of basal cell carcinoma or carcinoma in situ of the cervix)
17. Patients with the presence of active or suspected acute or chronic uncontrolled infection
18. Patients with a history of non-compliance to medical regimens or who are considered potentially unreliable or will be unable to complete the entire study
19. Patients with presence of Hepatitis B surface antigen (HbsAg)
20. Patients with presence of Hepatitis C antibody test (anti-HCV)

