#### **10.3.1.3 Laboratory abnormalities**

For laboratory tests covered by the National Cancer Institute - Common Terminology Criteria for Adverse Events (CTCAE) version 4.0, the study's biostatistical and reporting team will grade laboratory data accordingly. For laboratory tests covered by CTCAE, NCI-CTCAE v4.03 a Grade 0 will be assigned for all non-missing values not graded as 1 or higher. Grade 5 will not be used.

For laboratory tests where grades are not defined by NCI-CTCAE v4.03, results will be graded by the low/normal/high classifications based on laboratory normal ranges.

The following summaries will be generated separately for hematology, biochemistry and urinary laboratory tests:

- shift tables using NCI-CTCAE v.4 grades to compare baseline to the worst on-treatment value
- for laboratory tests where NCI-CTCAE v4.03 grades are not defined, shift tables using the low/normal/high/(low and high) classification to compare baseline to the worst on-treatment value.
- listing of all laboratory data with values flagged to show the corresponding NCI-CTCAE v4.03 grades and the classifications relative to the laboratory normal ranges.

In addition to the above mentioned tables and listings, other exploratory analyses, for example figures plotting time course of raw or change in laboratory tests over time or box plots might be specified in the MAP and/or SAP.

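### SAP 6.6.2 plans no by-visit level or change from baseline for HbA1c or fasting glucose, and the HbA1c shift table cannot show worsening in patients already above normal at baseline

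*SAP*

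**What the plan says.** SAP 6.6 names fasting plasma glucose and HbA1c among the safety assessments. SAP 6.6.2 then sets out the laboratory outputs: CTC-grade shifts from baseline to worst value for graded tests; for tests without a grade, "shift tables using the low/normal/high/ (low and high) classification will be produced/used to compare baseline to the worst on-treatment value"; and listings of all values with flags, with separate listings for grade 3 or 4. Liver tests, MDRD and corrected calcium get further rules of their own; HbA1c and FPG do not. By contrast, SAP 6.6.3 (vital signs) and 6.6.4 (ECG) both specify change from baseline at each post-baseline time point.

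Protocol 10.3.1.3 allowed for more, as an option: figures of the "time course of raw or change in laboratory tests over time or box plots might be specified in the MAP and/or SAP". SAP 6.6.2 specifies none.

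On the effect itself, Protocol 1.2.1.2 says of the earlier Phase III study (B2305) that "Hyperglycemia-related AEs appeared to be the most significant safety concern in terms of frequency of occurrence as well as overall clinical impact". It reports an "overall increase in HbA1c of" about 1.5% in both dose groups at 6 and 12 months, and adds: "Patients who had pre-existing diabetes had a higher degree of hyperglycemia". Protocol 5.2 excludes "Diabetic patients with poor glycemic control as evidenced by HbA1c" only above 8%.

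Protocol 6.5.2 attaches actions to fixed limits: intervention at FPG above 130 mg/dL or HbA1c of at least 6.5%; referral at FPG above 160 mg/dL or HbA1c above 7.5% despite adjusted therapy; discontinuation at consistently high FPG of at least 240 mg/dL or HbA1c of at least 10% despite management and dose reduction. It defines grade 3 hyperglycemia as FPG above 250 mg/dL.

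**The concern.** The effect expected from earlier data is a shift in level. A three-category table built on the laboratory normal range records only whether a patient crosses that range. Someone who starts above it has no higher category to move into. Patients with diabetes are the group in whom the protocol reports more hyperglycemia, and those with HbA1c above normal but no higher than 8% can enter.

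At stake is whether the final core-plus-extension report contains a planned estimate of how much HbA1c and FPG rise, when they rise, and how many patients reach the values on which the protocol itself acts. The primary endpoint is not touched.

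**Working it through.** There is no stated figure to reproduce; this is a check of what the specified tables can show.

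**Inputs from the documents.** HbA1c rise about 1.5%, read as percentage points (Protocol 1.2.1.2). Entry limit 8% (Protocol 5.2). HbA1c limits 6.5%, 7.5% and 10%; FPG limits 130, 160 and 240 mg/dL; grade 3 above 250 mg/dL (Protocol 6.5.2).

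**Assumptions.** HbA1c has no CTC grade (the documents show none). Its upper limit of normal (ULN) lies between 6.0% and 6.5% (the documents give none).

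**Step 1: HbA1c.** Add 1.5 points to a range of baseline values and classify each by low/normal/high, then by the protocol's limits. The low/normal/high result is the same at either assumed ULN.

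| Baseline → worst (%) | Low/normal/high | Protocol limits (<6.5; 6.5–7.5; >7.5 to <10; ≥10) |
|---|---|---|
| 5.5 → 7.0 | normal → high | first → second |
| 6.0 → 7.5 | normal → high | first → second |
| 6.6 → 8.1 | high → high | second → third |
| 7.0 → 8.5 | high → high | second → third |
| 7.5 → 9.0 | high → high | second → third |
| 8.0 → 9.5 | high → high | third → third |

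All four baselines above the assumed ULN show no shift. The protocol's limits would reveal three of the four. The last, which ends just under 10%, appears only in a summary of change. This is why both a change summary and a threshold table are needed.

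**Step 2: FPG.** The protocol treats glucose as graded, so the CTC-grade rule applies and not the low/normal/high rule. A patient above normal but below grade 3 at baseline still shifts if the worst value passes 250 mg/dL, so there is no strict ceiling. But a worst value of 245 mg/dL is at least 240 and not above 250: it reaches the protocol's figure without being grade 3. A grade-3 count therefore misses the band from 240 to 250 mg/dL.

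**Step 3: could the change be estimated?** The half-width of a 95% CI for a mean change is 1.96 × SD / √n. The documents give no SD, so 1.0 to 2.0 points is assumed. Take n = 64, and n = 57 after the 10% drop-out of Protocol 10.5 (64 × 0.9 = 57.6).

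| SD | n = 57 | n = 64 |
|---|---|---|
| 1.0 | 0.26 | 0.24 |
| 1.5 | 0.39 | 0.37 |
| 2.0 | 0.52 | 0.49 |

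A mean rise of 1.5 points would be clearly visible in the whole group. A subgroup a quarter of the size would have intervals twice as wide.

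**The case against.** A reader might infer that both tests are confined to shift tables and that worsening would go unseen. The documents do not support that.

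- **FPG is graded**, so the strict ceiling belongs to HbA1c alone.
- **Individual values remain available.** SAP 6.6.2 lists and flags every laboratory value and lists grade 3 and 4 values separately.
- **Adverse events carry part of the information.** Protocol 8.1.2 names hyperglycemia as an event of special interest, and SAP 6.6.1 tabulates such events by preferred term and maximum grade. A laboratory abnormality that requires therapy is an adverse event (Protocol 8.1.1), and the SAP tabulates events needing additional therapy, dose adjustment or discontinuation. The Phase III remark about the main safety concern is itself about these events, not about the two tests.
- **SAP 6.5.2, item 10, names blood glucose and HbA1c** in a list to be summarized at each scheduled assessment, and Protocol 10 gives general statistics for continuous variables.
- **The core-phase SAP and the Master Analysis Plan are not available here** and might contain such tables.

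The first two points stand in full and limit the finding. The others stand in part. Event counts and listings give no estimate, interval or time course. Item 10 names no statistic, and the Protocol 10 rule specifies neither visits nor change from baseline, so together they leave room for a by-visit summary without planning one. SAP 5.3 and 6.5.2 cite the core-phase SAP where they rely on it; SAP 6.6.2 does not, and this SAP is the combined plan for both phases. Outputs in the unseen documents cannot be ruled out.

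Two cautions also stand. Mean change will be blunted by antidiabetic treatment and by withdrawal at high values. And Protocol 10.3.1.3 requires the low/normal/high table for ungraded tests, so it must not be replaced.

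**Conclusion.** The point holds as a gap in specification. SAP 6.6.2 plans no by-visit level or change from baseline for HbA1c or FPG. If HbA1c is ungraded, its shift table cannot register worsening in any patient already above the ULN at baseline, and a rise of the size seen in the Phase III study leaves such a patient in the same cell. For FPG the gap is narrower: no level or change by visit, and a grade-3 boundary 10 mg/dL above the protocol's 240 mg/dL limit (250 − 240).

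How many patients this affects cannot be stated, because the documents give neither the HbA1c normal range nor its baseline distribution. The ceiling rests on HbA1c having no CTC grade; the worked examples also rest on an assumed ULN of 6.0% to 6.5%. The absence of a by-visit summary from 6.6.2 rests on neither. The change is worth making because it concerns a known effect of the drug and uses data already collected.

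**What to change.** Keep the present shift tables and listings, and add to SAP 6.6.2:

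1. HbA1c and FPG by visit, as level and change from baseline with 95% CI, overall and descriptively by diabetic status at baseline (diabetes history is collected under Protocol 7.1.1.3). State beside the table that antidiabetic treatment and withdrawal at high values will blunt the mean change.
2. A baseline-to-worst shift table on limits already in the protocol: HbA1c below 6.5%, 6.5 to 7.5%, above 7.5 to below 10%, and 10% or more; FPG up to 130, above 130 to 160, above 160 to below 240, and 240 mg/dL or more. Note that one worst value in the top category shows that the figure was reached, not that the discontinuation criterion, which requires consistently high FPG or HbA1c at that level despite management, was met. Because SAP 6.6.2 converts values to SI units, give the FPG limits in mmol/L as well: the protocol states 7.2 and 13.3 for 130 and 240 mg/dL, and the same ratio gives 160 × 13.3 / 240 = 8.9.

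The cost is two tables, with wide intervals in the diabetic subgroup. No clinical rule changes. The SAP was already extended after database lock to add the missed Karnofsky summary, so an addendum is a known route; outputs added that way should be labelled as added after lock. If item 10 of SAP 6.5.2 was meant to cover the by-visit summaries, naming the statistics there would settle the first addition.

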6.6.3 Vital signs and weight for core and extension phase

Vital signs (body temperature, sitting pulse, sitting blood pressure), weight and waist circumference will be summarized and listed. Patients with clinically notable vital sign values will be flagged in the listing.

Vital sign analysis will be summarized over core (baseline to week 35) and extension phase (week 43 to final cutoff) based on safety set. Study baseline will be used in analysis.

The criteria for clinically notable abnormalities are defined as follows:

- Systolic BP: ≥ 180 mmHg and an increase ≥ 20 mmHg from baseline
 ≤ 90 mmHg and a decrease ≥ 20 mmHg from baseline
- Diastolic BP: ≥ 105 mmHg and an increase ≥ 15 mmHg from baseline
 ≤ 50 mmHg and a decrease ≥ 15 mmHg from baseline
- Pulse rate: ≥ 120 bpm with increase from baseline of ≥ 15 bpm
 ≤ 50 bpm with decrease from baseline of ≥ 15 bpm
- Body temperature: $\geq 39.1^\circ\text{C}$

$\leq 35^{\circ}\text{C}$

- Weight: Increase from baseline of $\geq 10\%$
decrease from baseline of $\geq 10\%$

The following summaries will be produced for each vital sign parameter:

- Number (%) of patients with clinically notable abnormalities in Vital signs at any post- baseline time point
- Summary statistic for change from baseline to each post-baseline time points.

Baseline = last value prior to or on the first dose during the study. After baseline, the value closest to the target day (i.e. visit window mid - point) is analyzed if a patient had more than one value within a time window.

6.6.4 ECG

ECG analysis will be summarized over core (baseline to week 35) and extension (week 43 to final cutoff) phase based on safety set. Study baseline will be used in analysis.

The following analyses will be performed for RR, PR, QT intervals and QRS duration, ventricular rate, QTcB (Bazett's formula) and QTcF (Fridericia's formula):

- Summary statistics at baseline and all scheduled post-baseline time points until final cut-off date in extension phase
- Summary statistics of changes from baseline at each scheduled post-baseline time point until final cut-off date in extension phase
- Listing of ECG data (scheduled and unscheduled visits)

Number (%) of patients with a notable QT interval, based on both QTcB and QTcF will be summarized for extension phase on -treatment period separately. ECG shift table based on notable values will be summarized. Notable criteria for QTcB/QTcF include:

- >450 ms at any post-baseline time point and ≤ 450 ms at baseline,
- >480 ms at any post-baseline time point and ≤ 480 ms at baseline,
- >500 ms at any post-baseline time point and ≤ 500 ms at baseline,
- An increase from baseline > 30 ms at any post-baseline time point ,
- An increase from baseline > 60 ms at any post-baseline time point.

Patients with notable QT interval values and newly occurring qualitative ECG abnormalities will be flagged in the listings.

6.6.5 Gallbladder ultrasound

The findings of the gallbladder imaging (presence of gallstones, presence of sludge, dilatation of ductal system) will be summarized at each visit using frequency tables for safety set over core and extension phase.

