### **7.1.1 Screening**

The informed consent must be signed prior to ANY screening procedure being performed. Screening visit (Visit 1) should occur within 28 days prior to the baseline visit (Visit 2). The site should enter the Interactive Web Response System (IWRS) when a patient signs the informed consent and begins his/her screening. Patients that do not meet eligibility criteria are allowed to be rescreened and should use the same patient ID number. Rescreening should be documented in the source files.

If the following procedures meet all entry criteria at the original screening they do not have to be repeated for patients who rescreen within 60 days from the first day of the initial screening: vital signs, MRI, and gallbladder ultrasound. Any of these assessments that are abnormal and all other assessments not listed here are to be repeated.

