## 8 Safety monitoring and reporting

### 8.1 Adverse events

#### 8.1.1 Definitions and reporting

An adverse event is defined as the appearance of (or worsening of any pre-existing) undesirable sign(s), symptom(s), or medical condition(s) that occur after patient's signed informed consent has been obtained. Abnormal laboratory values or test results occurring after informed consent constitute adverse events only if they induce clinical signs or symptoms, are considered clinically significant, require therapy (e.g., hematologic abnormality that requires transfusion or hematological stem cell support), or require changes in study medication(s).

Adverse events that begin or worsen after informed consent should be recorded in the Adverse Events CRF. Conditions that were already present at the time of informed consent should be recorded in the Medical History page of the patient's CRF. Adverse event monitoring should be continued for at least 30 days following the last dose of study treatment. Adverse events (including lab abnormalities that constitute AEs) should be described using a diagnosis whenever possible, rather than individual underlying signs and symptoms. When a clear diagnosis cannot be identified, each sign or symptom should be reported as a separate Adverse Event.

Adverse events will be assessed according to the Common Terminology Criteria for Adverse Events (CTCAE) version 4.03. If CTCAE grading does not exist for an adverse event, the severity of mild, moderate, severe, and life-threatening, corresponding to Grades 1 - 4, will be used. CTCAE Grade 5 (death) will not be used in this study; rather, information about deaths will be collected through a Death form.

The occurrence of adverse events should be sought by non-directive questioning of the patient during the screening process after signing informed consent and at each visit during the study. Adverse events also may be detected when they are volunteered by the patient during the screening process or between visits, or through physical examination, laboratory test, or other assessments. As far as possible, each adverse event should be evaluated to determine:

1. The severity grade (grade 1-4)
2. Its duration (start and end dates or Ongoing at End of Study)
3. Its relationship to the study treatment (Reasonable possibility that AE is related: No, Yes)

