### **Gallbladder Ultrasound**

Gallbladder data at each visit will be summarized and listed.

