6.6.1 Adverse events (AE)

All adverse events and the cause of death, as recorded on the completion CRF pages, will be coded using the latest available version of the MedDRA coding dictionary that provides the system organ class (SOC) and preferred term (PT) information.

AEs will be graded according to the Common Terminology Criteria for Adverse Events (CTCAE) version 4.0.

The CTC/severity grade will not be imputed if missing. CTC grade 5 (death) will not be used in this study.

The incidence of treatment-emergent AEs, during the core phase and during the overall on- treatment period, will be summarized by system organ class (SOC), preferred term (PT) and severity (based on NCI-CTCAE v.4 grades), type of adverse event, relation to study treatment.

A patient with multiple occurrences of an AE will be counted only once in the respective AE category

The following selection of treatment-emergent AEs will be listed and summarized for safety set from study start to final cut-off date for safety set:

- AEs regardless of study drug relationship
- AEs suspected to be study drug-related
- SAEs regardless of study drug relationship
- AEs leading to study drug discontinuation, regardless of study drug relationship
- AEs leading to study drug discontinuation, suspected to be study drug-related
- AEs requiring dose adjustment or study-drug interruption, regardless of study drug relationship
- AEs requiring additional therapy, regardless of study drug relationship
- AEs excluding SAEs
- Adverse events of special interest by type

Specific groupings of AEs of special interest will be considered and the number of patients with at least one event in each grouping ("category") will be reported. Such groups consist of AEs for which there is a specific clinical interest in connection with pasireotide treatment (i.e. where pasireotide may influence a common mechanism of action responsible for triggering them) or AEs which are similar in nature (although not identical) within safety set. The specific groupings of AEs as defined in the latest documentation available prior to database lock (in [[Cabinets/CREDI Projects/S/SOM230B/Integrated Medical Safety/Safety Profiling and Signal detection/Signal detection]]).

The following table will be produced:

- AEs of special interest by type (any AE, AE suspected to be drug-related, SAE, AE leading to discontinuation, AE requiring dose adjustment), PT and maximum Common Terminology Criteria (CTC) grade.

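### The planned gallbladder ultrasound tables show findings by visit and do not separate those new on treatment from those present at screening

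*SAP*

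**What the plan says.** SAP 6.6.5 names three ultrasound findings ("presence of gallstones, presence of sludge, dilatation of ductal system") and says that they "will be summarized at each visit using frequency tables for safety set over core and extension phase". Protocol 10.3.1.4, under Gallbladder Ultrasound, says: "Gallbladder data at each visit will be summarized and listed". Neither text mentions a shift from baseline, a category for new findings, or a count over all post-baseline scans.

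A pre-dose scan exists. Protocol Table 7-1 schedules an ultrasound at screening. Section 7.1.1 confirms this, since the procedures that a rescreened patient may skip if they were acceptable at first are those of the "initial screening: vital signs, MRI, and gallbladder ultrasound". Further scans follow in the core phase, and Table 7-3 sets them every 24 weeks in the extension.

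The relevant exclusion in protocol 5.2 is "Patients with symptomatic cholelithiasis". Patients with silent stones or sludge may enter.

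On adverse events, SAP 6.6.1 plans to summarize "The incidence of treatment-emergent AEs, during the core phase and during the overall on- treatment period" by system organ class and preferred term. Protocol 10.3.1.2 counts as treatment-emergent those events that arise or get worse relative to baseline. Under protocol 8.1.1, abnormal laboratory values or test results "constitute adverse events only if they induce clinical signs or symptoms, are considered clinically significant, require therapy" or a change of study medication.

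**The concern.** Protocol 1.2.1.2 lists cholelithiasis among the adverse events seen in at least 10% of patients in the Phase III study ("diarrhea, nausea, abdominal pain, cholelithiasis, hyperglycemia"). A reader of the safety section will want to know how many patients who started with a clear gallbladder developed stones, sludge or duct dilatation on treatment. A by-visit frequency table counts an entry stone that is still there together with a stone that is new. It also misses the patient-level view over time: sludge seen at one scan and gone at the next counts at that visit only, so no single row gives the number of patients who ever had a new finding.

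Elsewhere the SAP does refer safety tests back to baseline. Section 6.6.2 gives laboratory tests, liver function and MDRD a shift from baseline to the worst later value. Section 6.6.4 requires the QTc threshold not to be exceeded at baseline and adds a shift table. Gallbladder imaging has no equivalent.

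**Working it through.** The documents give no gallbladder figure to reproduce and no baseline prevalence. The check therefore has two parts: which planned outputs could show new findings, and how far by-visit prevalence determines incidence. All counts below are assumed, except N = 64, the enrolment target in protocol section 5.

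**1. Which outputs show new findings?**

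- Ultrasound tables (SAP 6.6.5): presence by visit; entry and new findings pooled.
- Treatment-emergent adverse event tables (SAP 6.6.1): new or worsened events by preferred term, but only those reported as adverse events. A new finding that is silent, judged not clinically significant, and followed by no therapy or change of study medication need not be reported.
- Listing (protocol 10.3.1.4): holds the information patient by patient but does not tabulate it.

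No planned table gives the incidence of new ultrasound findings.

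**2. What two prevalences say about incidence, with complete follow-up**

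Let b be the number positive at screening, v the number positive at a later visit, and r the number of entry findings that have resolved by then. Then

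new findings = v − (b − r), and incidence = [v − (b − r)] / (N − b).

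Take N = 64, b = 13, v = 19, so N − b = 51.

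| Entry findings resolved (r) | New findings | Incidence among 51 |
|---|---|---|
| 0 | 19 − 13 = 6 | 6/51 = 11.8% |
| 2 | 19 − 11 = 8 | 8/51 = 15.7% |
| 4 | 19 − 9 = 10 | 10/51 = 19.6% |
| 6 | 19 − 7 = 12 | 12/51 = 23.5% |

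All four rows give the same by-visit table: 13 of 64, then 19 of 64. The upper limit, with all 13 entry findings resolved, is 19/51 = 37.3%, but that is an extreme case.

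**3. Drop-out**

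Suppose that 45 of the 64 have the later scan (45/64 = 70%) and 19 of them are positive. Let k be the number of those 45 who were positive at screening, and let all their findings persist. Then incidence among those seen = (19 − k)/(45 − k).

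- k = 13: 6/32 = 18.8%
- k = 6: 13/39 = 33.3%
- k = 0: 19/45 = 42.2%

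The by-visit table does not show k. Attrition of this order is plausible: protocol 2.1 reports that about 65% and 48% of patients in the registration study completed 6 and 12 months. Entry to the extension also depends on approval or reimbursement in the patient's country (protocol 4.1).

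**4. When is incidence identified?**

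With the screening row shown, no drop-out and no resolution, incidence = (later prevalence − screening prevalence)/(1 − screening prevalence). For example, 10% rising to 28% gives 0.18/0.90 = 20%, and 20% rising to 28% gives 0.08/0.80 = 10%. These are two different tables with two different answers. The ambiguity comes from resolution and drop-out, not from by-visit reporting alone.

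**The case against.** The case against acting is substantial.

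- **Reported cholelithiasis already has an incidence.** A reader might infer that the on-treatment incidence of gallstone disease cannot be read at all. The documents do not support that. Protocol 1.2.1.2 describes the effect as an adverse event, and the treatment-emergent tables by preferred term give that incidence without unchanged entry stones. A new stone that the investigator considers clinically significant is an adverse event even without symptoms. This stands, and it confines the gap to silent findings with no clinical consequence recorded.
- **The screening row helps.** A reader might also argue that one end-of-treatment prevalence, say 28%, fits either 10% at entry with 20% new or 20% at entry with 10% new. That holds only if the screening row is left out. SAP 6.6.5 says each visit, which naturally includes screening, and step 4 above shows that the two cases then differ. This stands; the argument needs resolution or drop-out.
- **The listing allows a hand count.** With about 64 patients it is feasible. SAP 6.6.5 does not repeat the listing, but does not withdraw it.
- **Incidence is not a stated purpose of the scans.** Protocol 7.2.2 lists ultrasound among several safety assessments, and 8.1.2 names hypocortisolism, hyperglycemia and QTc prolongation for targeted follow-up, not gallbladder events. It would go too far to say that the scans exist to yield this one figure.
- **The SAP follows the protocol**, in an exploratory, non-comparative study without formal testing.

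What remains is that none of these outputs is a table that separates new from pre-existing ultrasound findings.

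**Conclusion.** The point holds as a minor one. The planned ultrasound tables pool findings present at screening with findings new on treatment, and the adverse event tables need not capture new silent findings. In the illustration, one and the same by-visit table is compatible with 11.8% to 23.5% new findings when 0 to 6 of 13 entry findings resolve. With 45 of 64 patients seen, the range is 18.8% to 42.2%, depending on which patients remain.

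These ranges rest on assumed counts and show only that prevalence does not fix incidence; they do not predict the trial's result. The core-phase SAP cited as [4] and the document that defines the groupings of adverse events of special interest were not available, so a similar table or a gallbladder category there cannot be excluded. SAP 6.6.5, in the plan for the combined final analysis, neither contains nor cites one. The primary endpoint and the sample size are not affected.

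**What to change.** In SAP 6.6.5 add, for each of stones, sludge and duct dilatation:

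1. A shift table from the screening scan to the worst on-treatment scan, with a row and a column for missing scans.
2. Among patients negative for that finding at screening and with at least one on-treatment scan, the number and percentage with the finding at any on-treatment scan, for the core phase and for core plus extension.

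Keep the by-visit tables with the screening row shown, and state in 6.6.5 that the protocol's listing is retained.

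The cost is one extra table. Protocol 7.2.2.5.8 already has the results recorded in the CRF, so no new data are needed. The SAP's document history shows a descriptive safety summary (Karnofsky performance status) added after database lock, so there is precedent; an addition made at that stage should be dated and labelled in the same way.
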